### 5.3.1.6 Action Taken

Missing actions taken will remain missing and not be imputed.

### 5.3.2 Immunogenicity

For the computation of GMTs, any titer reported as < LLOQ will be converted to a value of 1/2 LLOQ.

While a single approach was used for GMTs, two different approaches for GMT ratios were applied:

- For Gardasil, < LLOQ will be converted to 1/2 LLOQ
- For CYD dengue vaccine, < LLOQ will be converted to 1/2 LLOQ for a numerator and < LLOQ will be converted to LLOQ for a denominator

Missing data will not be imputed. No test or search for outliers will be performed.

### 5.3.3 Efficacy

Not applicable.

## 5.4 Interim / Preliminary Analysis

No planned interim / preliminary analyses were performed.

## 5.5 Determination of Sample Size and Power Calculation

A total of 528 subjects was enrolled: 264 subjects in each group.

The reference standard deviations (SD) considered are the following for Gardasil: 0.6, 0.4, 0.5 and 0.5 for HPV-6, HPV-11, HPV-16 and HPV-18, respectively.

The reference seroconversion rates for Gardasil were set to 99% for all of the 4 antigens.

The reference SD considered are the following for the CYD dengue vaccine: 0.7 for serotypes 1 and 2, 0.5 for serotypes 3 and 4 (based on CYD studies conducted in Asia Pacific: CYD14, CYD23, CYD22 and CYD28).

Considering a potential attrition rate of 15%, such sample size would provide 222 evaluable subjects per group in the PPAs. This will give, for the co-primary objectives, a global power of 98.4% and for secondary objectives (in terms of Gardasil seroconversion) a power of 90.2%.

Following Protocol Amendment 1, the number of evaluable subjects may be difficult to achieve (considering only exposed/seropositive subjects at baseline to be included in the Per-Protocol populations). Thus the non-inferiority testing will be done only if the number of evaluable subjects provides a global power of at least 80% for the co-primary objectives and secondary objective i.e., if the number of evaluable subjects per group is at least 121 per group for the co-primary objectives and 194 per group for the secondary objective. The power for non-inferiority in terms of GMTs per antigen and serotype will be than as follows:

This sample size will also provide a 95% probability of observing an AE that has a true incidence of 1.1% in each group.

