### 3 Description of the Overall Trial Design and Plan

#### 3.1 Trial Design

This is a Phase IIIb, randomized, open-label, multicenter study in 528 subjects aged 9 to 13 years in Malaysia.

Subjects have been randomized in a 1:1 ratio into one of 2 following groups, stratified by gender in a 2:1 (female:male) ratio to receive:

- Group 1 (N=264): 3 doses of CYD dengue vaccine and 2 doses of Gardasil® (Human Papillomavirus Quadrivalent [Types 6, 11, 16, and 18] Vaccine, Recombinant) concomitantly to the first 2 doses of CYD dengue vaccine
- Group 2 (N=264): 3 doses of CYD dengue vaccine and 2 doses of Gardasil sequentially to the first 2 doses of CYD dengue vaccine

For both vaccines, each dose is to be administered 6 months apart.

As per Protocol Amendment 1, only subjects identified as dengue immune (seropositive) before administration of the first CYD dengue injection (at V01 for Group 1 and at V02 for Group 2) and who consented to receive the remaining injection of dengue vaccine could remain in the study as per initial study procedures.

Subjects identified as non-immune (seronegative) at baseline could continue in the study for a 6-month safety follow-up. They did not receive any further CYD dengue vaccine injection and had a blood sample for the assessment of HPV antibodies after the 2 doses of Gardasil if they returned in study for M7 (Visit 5).

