## 5.1 Statistical Methods

In a general way, non-inferiority testing will be performed on dengue immune subjects. The tests will be done only if the number of evaluable subjects provides a global power of at least 80% for the co-primary objectives and secondary objective. In case the global power is insufficient to perform non-inferiority testing, only descriptive analyses will be performed.

Only descriptive analyses will be conducted in dengue non-immune subjects and in the overall population.

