#### **Individual hypotheses on CYD response for each antigen:**

A non-inferiority testing approach will be used to compare GMTs 28 days after the third injection of CYD dengue vaccine between groups for each serotype “i” based on the following individual hypotheses:

$$H_0^i: \text{GMT}_{\text{Group1}}^i / \text{GMT}_{\text{Group2}}^i \leq \frac{1}{\delta} \Leftrightarrow \log_{10}(\text{GMT}_{\text{Group1}}^i) - \log_{10}(\text{GMT}_{\text{Group2}}^i) \leq -\log_{10}(\delta)$$

$$H_1^i: \frac{1}{\delta} < \text{GMT}_{\text{Group1}}^i / \text{GMT}_{\text{Group2}}^i > \frac{1}{\delta} \Leftrightarrow \log_{10}(\text{GMT}_{\text{Group1}}^i) - \log_{10}(\text{GMT}_{\text{Group2}}^i) > -\log_{10}(\delta)$$

with:

i, serotypes in {1, 2, 3, 4}

$\delta$  non-inferiority limit is set at 2 ie, 0.301 ( $=\log_{10}[2]$ ), for each serotype “i”

Non-inferiority for serotype i will be demonstrated if the lower bound of the 2-sided 95% CI is greater than  $-\delta$ .

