#### **Global hypotheses for non-inferiority on CYD response:**

$H_0^G: \text{at least one } H_0^i \text{ not rejected}$

$H_1^G: \text{all } H_0^i \text{ are rejected}$

Overall, non-inferiority among the groups will be demonstrated if, for each antigen of Gardasil and each serotype of CYD dengue vaccine, the 2-sided 95% CIs lie above  $-\delta$ .

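### The minimum of 121 evaluable subjects per group matches the 80% global power condition only for equal groups, so it can cancel the co-primary tests when that condition is met

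*SAP*

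**What the plan says.** SAP 5.1 gives the condition as power: "The tests will be done only if the number of evaluable subjects provides a global power of at least 80" per cent; otherwise the analysis is descriptive. Protocol 12.1 says the same, also without a count, and the Statistical Methods part of the protocol synopsis makes it an if-and-only-if condition.

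SAP 5.5, Protocol 12.5 and the sample-size part of the synopsis then restate the condition, introduced by i.e., as a count: "if the number of evaluable subjects per group is at least 121 per group for the co-primary objectives and 194 per group" (the second number belongs to the secondary objective). SAP Table 5.2 and Protocol Table 12.1 calculate power for 222 and for 121 subjects in each group, that is, for equal groups only.

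Neither document says what happens if one group is below 121 and the other above it. Neither mentions a total or a recalculation at the observed group sizes.

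**The concern.** The power of a comparison of two means depends on 1/n1 + 1/n2. The count rule looks only at the smaller group. If one group has 120 evaluable subjects and the other 140, SAP 5.1 read with Protocol 12.1 leads to testing, while SAP 5.5 leads to description only.

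Equal groups can no longer be assumed. "Subjects have been randomized in a 1:1 ratio into one of 2 following groups", stratified by gender, but dengue immune status was not a stratum. The evaluable sets are now the dengue-immune subjects left after per-protocol exclusions, and the protocol synopsis says that the number of exposed subjects per group was unknown at Amendment 1.

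This rule alone decides whether the trial delivers a non-inferiority conclusion or only descriptive results. If the conflict were resolved after titres had been compared in an open-label trial, the choice would look data-driven.

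**Working it through.** **Inputs from the documents**
- Test: "Non-inferiority for serotype i will be demonstrated if the lower bound of the 2-sided 95% CI is greater than" minus the margin, so one-sided alpha is 0.025 per endpoint.
- Margin: "non-inferiority limit is set at 2 ie, 0.301" on the log10 scale, the same for the HPV antigens.
- HPV SDs: "The reference standard deviations (SD) considered are the following for Gardasil: 0.6, 0.4, 0.5 and 0.5 for HPV-6, HPV-11, HPV-16 and HPV-18, respectively".
- Dengue SDs: "0.7 for serotypes 1 and 2, 0.5 for serotypes 3 and 4".
- Success: "Overall, non-inferiority among the groups will be demonstrated if, for each antigen of Gardasil and each serotype of CYD dengue vaccine", the confidence interval lies above the negative margin, so all eight comparisons must pass.

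**Assumptions**
- The true difference is 0. This is not stated, but it reproduces the table.
- The endpoints are independent, so global power is the product of eight powers. The plan's own figure implies this.

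**Formula.** For each endpoint, SE = SD × √(1/n1 + 1/n2). Power is the probability that a non-central t variable with n1 + n2 − 2 degrees of freedom and non-centrality 0.301/SE exceeds the 97.5% t quantile.

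**The plan's figure, 121/121.** Here 1/121 + 1/121 = 0.01653.
- SD 0.7: SE 0.0900, non-centrality 3.345, power 91.5%.
- SD 0.6: SE 0.0771, non-centrality 3.902, power 97.3%.
- SD 0.5: SE 0.0643, non-centrality 4.682, power 99.7%.
- SD 0.4: SE 0.0514, non-centrality 5.853, power above 99.9%.

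The product of the table's rounded entries is 0.973 × 0.999 × 0.997⁴ × 0.915² = 80.4%, as printed. Unrounded it is 80.3%. At 120/120 it is 79.8%, so 121 is right for equal groups. At 222/222 it is 98.9%; the printed 98.4% is 0.999⁶ × 0.995², which takes each entry shown as above 99.9 as 99.9.

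**Unequal groups, same formula**

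| n1/n2 | 1/n1 + 1/n2 | Global power | Meets 80% | Meets 121 per group |
|---|---|---|---|---|
| 121/121 | 0.01653 | 80.3% | yes | yes |
| 120/122 | 0.01653 | 80.3% | yes | no |
| 118/124 | 0.01654 | 80.3% | yes | no |
| 112/132 | 0.01650 | 80.4% | yes | no |
| 120/140 | 0.01548 | 84.3% | yes | no |

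The 118/124 split has the same total as 121/121 (242). The 120/140 split has 18 more subjects and more power, yet it fails the count.

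**How often the rules would disagree.** The evaluable share is not in the documents. Assume that each arm's evaluable count is binomial with 264 subjects and share p, and that the same counts serve all eight endpoints.

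| p | Expected per group | 80% power met | 121 per group met | 80% met but count failed |
|---|---|---|---|---|
| 0.42 | 111 | 4% | 1% | 3% |
| 0.44 | 116 | 22% | 9% | 13% |
| 0.47 | 124 | 72% | 45% | 27% |
| 0.50 | 132 | 98% | 85% | 13% |
| 0.52 | 137 | over 99% | 96% | 4% |
| 0.55 | 145 | about 100% | about 100% | 0.2% |

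**Direction.** If both groups have at least 121, then 1/n1 + 1/n2 is at most 2/121 and power is at least that of 121/121. The count rule therefore never admits a test below 80%.

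**The case against.** The strongest reply is that the power condition already stands without a count in SAP 5.1 and Protocol 12.1, that 121 appears beside tables for equal groups, and that an analyst could compute power at the observed numbers. It may be added that the wording in SAP 5.1 makes 80% necessary but not sufficient, so a stricter count does not contradict it. The first part stands as far as it goes: this is a conflict of wording, and 121 and 80.4% are correct for equal groups. The second part does not hold. The synopsis makes the power condition sufficient as well as necessary, and SAP 5.5 offers the count as a restatement, not as an extra requirement.

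It also stands that the error is on the safe side and that, if the tests were dropped, GMTs with 95% confidence intervals would still be reported by group (SAP 5.1.2.2). The formal conclusion would nevertheless be lost.

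Two extensions are tempting and should not be made:
- A harmonic mean of at least 121 is not the same as 80% power. The splits 120/122, 118/124 and 116/126 have harmonic means of 120.99, 120.93 and 120.79, yet give 80.3%, 80.3% and 80.2%. Such a rule would repeat the fault.
- The minimum of 194 for the secondary objective shares the per-group wording, but it rests on seroconversion rates and the Newcombe-Wilson interval, not on SDs. The figures here do not carry over, and that minimum is not judged.

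**Conclusion.** The point holds for the co-primary objectives. The count of 121 per group and the 80% power condition are presented as one rule but lead to opposite decisions for modestly unequal groups.

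A reader might infer that chance imbalance will cancel the co-primary tests. The documents do not support that. Under the binomial assumption the rules disagree materially only for an evaluable share of about 42% to 52% of each arm (about 111 to 137 subjects), with a peak of about 27% of trials near 47%. At 55% and above they practically always agree, and the documents do not say where the trial lies. What they do show is that the sponsor foresaw a shortfall and set 121 as the decision point, so the rule should be unambiguous near that value.

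The power figures rest on a zero true difference, independent endpoints and the plan's reference SDs.

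**What to change.** In SAP 5.5, Protocol 12.5 and the synopsis, replace the minimum of 121 per group for the co-primary objectives with: global power of at least 80%, computed by the method of Table 5.2 with its reference SDs and margin at the observed evaluable numbers in each group, using PPG counts for the HPV antigens and PPC counts for the dengue serotypes. Both sets must be named because SAP 5.2.5 tests the two vaccines on different sets, with different exclusions.

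Name the calculation as well: non-central t, zero true difference, product of the eight powers. The choice matters at the boundary, since the normal approximation gives 80.3% at 120/120 and the t version 79.8%. Keep 121 only as the equal-group example. Leave the minimum of 194 out of this wording; any change there needs its own calculation with the Newcombe-Wilson method.

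The cost is one sentence in each place and no subjects. The rule uses only sample sizes, so the type I error of the tests is unaffected, provided that it is fixed before titres are compared.

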**Table 5.2: Powers for Non-inferiority between GMT for each antigen and serotype**

| Antigen/Serotype    | Alpha | $\delta$ | References
SD(s) | Power (%) for
222 evaluable
subjects per
group | Power (%) for
121 evaluable
subjects per
group |
|---------------------|-------|----------|---------------------|---|---|
| HPV-6               | 0.025 | 0.301    | 0.6                 | > 99.9  | 97.3  |
| HPV-11              | 0.025 | 0.301    | 0.4                 | > 99.9  | > 99.9  |
| HPV-16              | 0.025 | 0.301    | 0.5                 | > 99.9  | 99.7  |
| HPV-18              | 0.025 | 0.301    | 0.5                 | > 99.9  | 99.7  |
| Dengue serotype 1   | 0.025 | 0.301    | 0.7                 | 99.5  | 91.5  |
| Dengue serotype 2   | 0.025 | 0.301    | 0.7                 | 99.5  | 91.5  |
| Dengue serotype 3   | 0.025 | 0.301    | 0.5                 | > 99.9  | 99.7  |
| Dengue serotype 4   | 0.025 | 0.301    | 0.5                 | > 99.9  | 99.7  |
| Global power |       |          |                     | 98.4%  | 80.4%  |

**Table 5.3: Powers for Gardasil seroconversion for each antigen**

| Antigen             | Alpha | $\square$ | Power (%) for 222 evaluable subjects per group | Power (%) for 194 evaluable subjects per group |
|---------------------|-------|-----------|--|--|
| HPV-6               | 0.025 | 5%        | 97.4   | 94.6   |
| HPV-11              | 0.025 | 5%        | 97.4   | 94.6   |
| HPV-16              | 0.025 | 5%        | 97.4   | 94.6   |
| HPV-18              | 0.025 | 5%        | 97.4   | 94.6   |
| Global power |       |           | 90.2%                                   | 80%  |

This sample size will also provide a 95% probability of observing an AE that has a true incidence of 1.51% in each group.

## **5.6 Data Review for Statistical Purposes**

A review of the data is anticipated through the data review process led by Data Management before each database lock.

## **5.7 Changes in the Conduct of the Trial or Planned Analyses**

According to Protocol amendment 1, the study population for the non-inferiority is reduced to the dengue immune subjects (seropositive) compared to initial sample size.

The results for immunogenicity and safety will be presented by baseline dengue status.

